### Exploratory Quantitative Analysis of START-C2H survey data:

Our community randomized trial consists of clustered data with participants nested within counties. To account for this "doubly-repeated" measures design, we will analyze all results using generalized linear mixed models. The covariance matrix for all observations within a county may be written as the Kronecker product of the compound symmetric covariance matrix for participants nested within county and a 2 by 2 residual covariance matrix for repeated measures nested within participants. Implementing the covariance model can be done in both PROC MIXED (for continuous measures) and PROC GLIMMIX (for categorical measures) in SAS by specifying a random intercept for county, and a compound symmetric residual matrix across time (repeated measures within participant). To estimate change in our primary outcomes due to the intervention we will begin by analyzing models of the following form:  $g(y) = \beta_0 + \beta_1 Time + \beta_2 Int + \beta_3 Time * Int$  where  $g()$  represents the appropriate link function for outcome  $y$ ,  $Time$  is a pre-post indicator variable, and  $Int$  is an indicator for the intervention group. The parameter of primary interest is  $\beta_3$ , the difference in slope between the intervention and control group. While our primary outcomes can be approximated as normally distributed, the link function  $g()$  will be modified as necessary to properly model the distribution for each outcome.

**Missing Data.** We will use multiple imputation to account for non-response over time and potential attrition. Additional augmentation variables found to be predictive of missingness will also be included in the imputation model. Ten imputations will be implemented. Additionally, we will use multiple imputation by chained equations to allow for imputation of non-normally distributed variables. All imputation analyses will be done using PROC MI and PROC MIANALYZE in SAS.

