**Power.** We estimated the statistical power to preliminarily detect a change in our outcomes using PROC GLMPOWER in SAS v9.4., accounting for autocorrelation within participants and nesting within counties. We estimate power for a multivariate model equivalent to our planned repeated measures models previously described. Because these analyses are exploratory (due to the smaller-than-anticipated sample size), we set the alpha to 0.10. Based on existing data, we assume a within-county ICC of 0.05 and a within-person autocorrelation of 0.35. We estimate power for all outcomes as approximately Gaussian. We further assume a type-1 error rate of 0.10, 12 counties, and 20 participants per county. At these sample sizes and with an exploratory p-value=0.10, we achieve statistical power of 0.80 for standardized mean of 0.55, or moderate sized effects with an alpha=0.10.

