Triangulating across qualitative and quantitative findings: We will use joint displays to systematically compare and contrast qualitative and quantitative findings for each intervention component/outcome relationship (e.g., preliminary [i.e.,  $p < 0.10$ ] hypothesis test results about the relationship of receiving FTS to subsequent overdose vs. qualitative grounded theory about this same relationship). When qualitative and quantitative findings both suggest an ameliorative relationship, we will conclude that the available evidence supports a beneficial effect. When both find an adverse relationship, we will conclude that the evidence indicates a harmful effect. When neither suggests a relationship, we will conclude that the evidence indicates no effect. When quantitative and qualitative results diverge, we will return to the qualitative and quantitative data to learn if we can resolve this discrepancy. Qualitative data may illuminate an unexpected confounder for the quantitative hypothesis test. Alternatively, qualitative data may suggest that the intervention only has an effect in one subgroup (e.g., individuals residing in counties with more services) and the quantitative findings reach a null conclusion because the quantitative sample is small, and includes both people who do and do not live in such counties. We will seek to systematically explore all divergences using these tables, and seek to refine relational statements and grounded theories accordingly. We will rely solely on qualitative data to learn whether the intervention effect is attenuated in a subgroup (e.g., women), given that the quantitative sample is underpowered to detect effect moderation.

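### With ten imputations, an outcome whose long-run p-value lies near 0.10 can change side of the threshold with the random seed

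*Combined protocol and SAP*

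**What the plan says.** The Missing Data paragraph, under Exploratory Quantitative Analysis of START-C2H survey data, plans multiple imputation by chained equations in SAS for non-response and attrition. It allows extra variables that predict missingness into the imputation model and fixes the number: "Ten imputations will be implemented". It gives no seed, no expected amount of missing data and no check of Monte Carlo error.

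The Power paragraph sets the threshold: "Because these analyses are exploratory (due to the smaller-than-anticipated sample size), we set the alpha to 0.10".

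The triangulation paragraph at the end of the SAP describes the p<0.10 results as preliminary and sets them beside the qualitative findings: "When qualitative and quantitative findings both suggest an ameliorative relationship, we will conclude that the available evidence supports a beneficial effect". Two adverse findings lead to a conclusion of harm, and two null findings to a conclusion of no effect. When the two sources disagree, the team goes back to both data sets to try to resolve the discrepancy.

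**The concern.** A p-value from multiple imputation is itself a random quantity: the same data with another seed give another p. How much it moves depends on the number of imputations and on the fraction of missing information (FMI). A number that is adequate for the point estimate may still be small when the p-value is compared with a fixed cut-off.

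Here a cut-off is applied outcome by outcome and feeds a categorical statement. For an outcome near the line, whether the joint display shows agreement or divergence could be decided by the seed rather than by the data. A re-run by another analyst might not reproduce the stated conclusion.

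**Working it through.** **Inputs from the documents.** Ten imputations; alpha 0.10; "12 counties, and 20 participants per county", so 240 people, or 120 per condition at 1:1; "we assume a within-county ICC of 0.05 and a within-person autocorrelation of 0.35". The target is the time-by-intervention interaction.

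**Assumed.** A two-sided test; data missing at random; 238 complete-data degrees of freedom (240 − 2); and the FMI, which the documents do not give. A simulation with 12 counties of 20, follow-up imputed from baseline and arm, gave FMI of about 0.07, 0.15, 0.23, 0.31 and 0.41 for 10%, 20%, 30%, 40% and 50% missing follow-up.

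**The plan's own figure.** The plan states: "we achieve statistical power of 0.80 for standardized mean of 0.55".
- SD of change = √(2 × (1 − 0.35)) = 1.140.
- Design effect = 1 + (20 − 1) × 0.05 = 1.95.
- Standard error = 1.140 × √(2/120 × 1.95) = 0.2055.
- Noncentrality = 0.55 / 0.2055 = 2.68.
- On 10 degrees of freedom (12 counties − 2) at two-sided 0.10, power = 0.801.

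The stated power is reproduced under a two-sided test, but it makes no allowance for missing data or imputation noise.

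**Noise in the test statistic.** Take the limiting standard error as 1. The pooled estimate varies between seeds with SD √(FMI/m). The estimated between-imputation variance also varies. Together, approximately:

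SD of t across seeds ≈ √( FMI/m + (t × FMI/2)² × 2/(m − 1) ).

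Worked case: FMI 0.23 and limiting p = 0.08, so t = 1.76.
- m = 10: SD = √(0.023 + 0.0410 × 2/9) = √0.0321 = 0.179. The pooled t centres on 1.76/√1.023 = 1.740. The critical value on about 80 Barnard-Rubin degrees of freedom is 1.664. Gap 0.076; 0.076/0.179 = 0.42; about 34% of seeds fall on the other side.
- m = 100: SD = √(0.0023 + 0.0410 × 2/99) = √0.0031 = 0.056. Centre 1.758, critical value 1.654, gap 0.104; 0.104/0.056 = 1.86; about 3%.

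Simulating Rubin's rules directly gives, for limiting p = 0.08, the share of seeds with p ≥ 0.10:

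| FMI (missing follow-up) | m = 10 | m = 100 |
|---|---|---|
| 0.15 (20%) | about 26% | about 1% |
| 0.23 (30%) | about 32% | about 3% |
| 0.31 (40%) | about 37% | about 6% |

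A separate, smaller simulation with only 25 data sets per attrition rate gave 32%, 35% and 42% with m = 10, and 6% to 11% with m = 100. These are somewhat higher but of the same order.

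**How far the effect reaches (FMI 0.3, m = 10).** Share of seeds with p < 0.10, by limiting p:

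| Limiting p | 0.03 | 0.05 | 0.08 | 0.10 | 0.12 | 0.15 | 0.20 |
|---|---|---|---|---|---|---|---|
| p < 0.10 | 98% | 90% | 63% | 44% | 28% | 13% | 3% |

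**All outcomes, not only borderline ones.** With m = 10 and FMI 0.1 to 0.5, two seeds disagree for 2.5% to 6.7% of outcomes under the null, 4.9% to 14.0% at about 50% power and 3.5% to 10.9% at about 80% power. At FMI 0.3:

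| m | Null | About 50% power | About 80% power |
|---|---|---|---|
| 10 | 4.8% | 9.8% | 7.2% |
| 20 | 3.4% | 6.8% | 4.8% |
| 50 | 2.1% | 4.2% | 3.0% |
| 100 | 1.5% | 2.9% | 2.1% |

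**Validity.** With m = 10 the rejection rate under the null is 0.097 to 0.098 against a nominal 0.10. Relative efficiency, 1/(1 + FMI/m), runs from 1/1.01 = 0.990 to 1/1.05 = 0.952.

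**What a change of side does in the joint display.** The seed alters only the quantitative entry.

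| Qualitative finding | p < 0.10, same direction or beneficial | p ≥ 0.10 |
|---|---|---|
| Ameliorative | Beneficial effect | Divergence |
| None | Divergence | No effect |

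One side of every change is the divergence step.

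**The case against.** The strongest reply is that the analysis is labelled exploratory, the p<0.10 results are called preliminary, and the test with ten imputations is valid: type I error holds and the efficiency loss is 1% to 5%. All of that stands and keeps the point minor. It does not answer the reproducibility question, because categorical conclusions are still drawn from the threshold.

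Second, no attrition is stated, so the documents alone cannot show that ten is too few. With little missing information, or with imputation variables that also predict the outcome well, the noise shrinks. This stands too. But even at FMI 0.1, an outcome with limiting p = 0.08 crosses in about 18% of seeds with ten imputations, against 0.1% with 100.

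Third, more imputations do not rescue an outcome whose limiting p is exactly 0.10; it stays close to a coin toss. True, but the spread narrows: at FMI 0.3, 95% of seeds give p between 0.042 and 0.221 with ten imputations, and between 0.077 and 0.129 with 100.

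A reader might go further and infer that another seed could turn a beneficial effect into no effect. The triangulation rule does not allow that: the first conclusion needs both sources to show benefit, the second needs neither to show a relationship, and the qualitative finding does not change with the seed.

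**Conclusion.** The point holds in a limited form. With ten imputations and no stated seed, an outcome whose limiting p is near 0.10 may enter or leave the divergence step by chance: about 26% to 37% of seeds for limiting p = 0.08, falling to about 1% to 6% with 100 imputations. This rests on an assumed FMI of 0.15 to 0.31, a two-sided test and data missing at random.

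Two broader readings are not supported. One is that results in general depend on the seed: two seeds agree for about 86% to 97.5% of outcomes, and those well away from 0.10 are stable. The other is that ten imputations make the test invalid or biased: the type I error is preserved. For an analysis declared exploratory, this is a minor improvement in precision and reproducibility.

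**What to change.** In the Missing Data paragraph, replace the sentence that sets ten imputations with one that specifies 100 (or at least 50, raised according to the observed fraction of missing information). Add that the seed is recorded before the analysis and that the Monte Carlo error is reported for any p-value near 0.10. The parts do different work: the larger number reduces the noise, the recorded seed makes a re-run repeatable, and the reported error shows the reader which results remain borderline.

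The cost is one amended passage in the SAP and a few minutes of computing. Nothing in data collection or the analysis model changes.

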#### COVID-19 Policies

We are changing the trial duration from three years to two years. To accommodate this shorter time period, we are modifying the study design from a stepped-wedge trial to a case crossover trial. We will randomize the 12 counties to two groups of six counties each versus three groups of four counties each. All counties will start at the same time. During months 1-6, counties randomized into Group 1 will receive the intervention, while counties randomized to Group 2 will serve as the comparison group. In Months 7-12, Group 1 counties will shift to the comparison group, and Group 2 counties will receive the intervention. In Months 13-18 we will conduct follow-up assessments in all counties. Months 19-24 will be devoted to data analysis and dissemination of the findings.

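### The 0.80 power at 0.55 SD is stated for all outcomes, but it does not carry over to uncommon binary outcomes

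*Combined protocol and SAP*

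**What the plan says.** The Power paragraph (SAP, Statistical Design and Power) sets its inputs as follows: "we assume a within-county ICC of 0.05 and a within-person autocorrelation of 0.35", and "We further assume a type-1 error rate of 0.10, 12 counties, and 20 participants per county". It concludes that "we achieve statistical power of 0.80 for standardized mean of 0.55, or moderate sized effects with an alpha=0.10". The scope is explicit: "We estimate power for all outcomes as approximately Gaussian".

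The analysis text above it is narrower. It says that the primary outcomes are close enough to normal, that the link function will be changed where an outcome needs it, and that the software will be PROC MIXED for continuous measures and "PROC GLIMMIX (for categorical measures". So non-Gaussian outcomes are foreseen, but none has its own power figure.

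The paragraph on triangulating qualitative and quantitative findings gives, as its example of a hypothesis test at p < 0.10, "the relationship of receiving FTS to subsequent overdose". It also sets a decision rule: where neither the quantitative nor the qualitative data point to a relationship, the team will conclude that there is no effect.

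Two other places bear on overdose. The Comparison Condition section and the benefits text for the comparison group both place overdose outside the primary outcomes. The background section says that large shares of people who use drugs still overdose, without giving a number.

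**The concern.** A standardized effect means something different for a yes/no outcome than for a continuous score. The SD of a binary outcome is fixed by its risk, and a reduction cannot exceed that risk. For an uncommon harm, a 0.55 SD reduction can therefore be more than the intervention could achieve by abolishing the harm. A more realistic effect, such as halving, is a much smaller fraction of an SD and has much lower power.

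What is at stake is how a null result is read. A reader of the Power paragraph would credit every tested outcome with 0.80 power for a moderate effect. Under the triangulation rule, a non-significant test together with silent qualitative data becomes a finding of no effect. For an uncommon binary harm, non-significance is the likely result even if the intervention halves the risk.

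**Working it through.** **Inputs from the documents.** Alpha 0.10 ("we set the alpha to 0.10"), 12 counties of 20 participants, ICC 0.05, within-person correlation 0.35, effect 0.55 SD. The COVID-19 Policies text under Study Design gives an even split: "We will randomize the 12 counties to two groups of six counties each".

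**My assumptions.** Two-sided test; parallel comparison of 6 against 6 counties, so 120 per arm; t distribution with 12 − 2 = 10 degrees of freedom. The settings of the plan's power procedure are not given. Base risks of 5% to 30% are also assumed.

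**1. Reproduce the plan's figure.**
- Design effect: 1 + 19 × 0.05 = 1.95. Effective n per arm: 120 / 1.95 = 61.5.
- SE of the difference in change, in SD units: sqrt(2 × 2 × (1 − 0.35) × 1.95 / 120) = 0.2055.
- Noncentrality: 0.55 / 0.2055 = 2.68. Power on 10 df, two-sided alpha 0.10: **0.801**.

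The stated 0.80 is confirmed for a continuous outcome, and these settings are a plausible reading of how it was obtained.

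**2. When is a 0.55 SD reduction possible for a binary harm?** Let p be the comparator risk. The largest possible reduction is p, with the treated risk at 0.
- SD from the comparator risk, sqrt(p(1 − p)): the condition p ≥ 0.55 × sqrt(p(1 − p)) gives p ≥ 0.3025 / 1.3025 = **0.232**.
- Variance averaged over the arms, p(1 − p)/2: p ≥ 0.15125 / 1.15125 = **0.131**.
- SD from the pooled risk p/2: p ≥ 0.15125 / (1 + 0.15125/2) = **0.141**.

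The bound is therefore about 13% to 23%, depending on the SD. It concerns reductions in a harm only.

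**3. Power for a binary outcome with the same inputs.** Both arms start at p; the comparator stays at p and the intervention arm falls to p₂. With v₀ = p(1 − p) and v₁ = p₂(1 − p₂),

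SE² = [2v₀(1 − 0.35) + v₀ + v₁ − 2 × 0.35 × sqrt(v₀v₁)] / 61.5.

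Example, 10% halved to 5%: v₀ = 0.0900 and v₁ = 0.0475. The bracket is 0.1170 + 0.0917 = 0.2087, so SE = 0.0582 and noncentrality = 0.05 / 0.0582 = 0.86. Power is 0.21.

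| Base risk | 0.55 SD (comparator SD) | Power, risk halved | Power, risk abolished |
|---|---|---|---|
| 5% | 12.0 points | 0.15 | 0.30 |
| 10% | 16.5 points | 0.21 | 0.49 |
| 20% | 22.0 points | 0.33 | 0.78 |
| 30% | 25.2 points | 0.47 | 0.93 |

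In this calculation even complete elimination reaches 0.80 power only from a base risk of about 21%.

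**4. Sensitivity.**
- Follow-up comparison only, normal approximation, same design effect: power for halving is 0.18, 0.28, 0.46 and 0.64 at 5%, 10%, 20% and 30%.
- Latent logistic scale: 0.55 SD is an odds ratio of exp(0.55 × π / √3) = 2.7, which is possible at any risk. Difference-in-change power on 10 df is then 0.18, 0.26 and 0.40 at 5%, 10% and 20%.
- Crossover form, 10 participants per county-period, between-period correlation ratio assumed to be 0.8 (not in the documents): power for halving is 0.29 at 10% and 0.49 at 20%.

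None of these reaches 0.80.

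**The case against.** The strongest reply is that the Power paragraph should be read together with the model text. That text claims normality for the primary outcomes, which gives the Gaussian calculation a natural scope. Overdose is not primary, and the analyses are labelled exploratory. The overdose example in the triangulation paragraph is also about receiving test strips, a component exposure, whereas the power figure is for the arm-by-time term. These points limit the consequence. They do not remove the problem, because the scope sentence says all outcomes, the same plan foresees categorical ones, and overdose is named as something to be tested at p < 0.10.

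Three stronger readings are tempting, and the documents do not support them.
- A reader might infer that the stated power cannot apply to overdose. That needs overdose to be binary with a risk below the bound. The documents give neither its coding nor its risk, the background suggests that overdose is frequent, and a count outcome would not be subject to the bound at all.
- A reader might take 23% as a fixed limit below which a 0.55 SD effect cannot exist. It falls to 13% or 14% with other SDs, and on the link scale, where such outcomes would be modelled, the effect is possible but poorly powered.
- A reader might conclude that tests of uncommon outcomes would be non-significant whatever the truth. The table contradicts this: abolishing a 20% risk has 0.78 power in the parallel form, and 0.95 in the crossover form with the assumed ratio of 0.8.

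The triangulation paragraph does recognise that a null may reflect a small sample, but only where the two sources diverge. Where both are null, nothing guards the conclusion.

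**Conclusion.** The point holds in conditional form. The 0.80 figure is arithmetically sound for an approximately continuous outcome and is stated more widely than the plan's own modelling text supports. For a binary harm with comparator risk below about 13% to 23%, a 0.55 SD reduction on the risk scale exceeds the whole risk. Across assumed base risks of 5% to 30%, power to detect a halving is about 0.15 to 0.47 in the parallel form on 10 df. The exact values depend on that form, the degrees of freedom and the assumed risks; the shortfall from 0.80 remains in every variant above. Because the analyses are exploratory and overdose is not primary, this is a correction to the power statement and to the reading of null results, not a challenge to the design.

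**What to change.** Three changes to SAP wording:

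1. In the Power paragraph, restrict the statement of 0.80 power at 0.55 SD to approximately continuous outcomes.
2. For each binary outcome to be tested, state its coding and assumed base risk, and add a line giving the detectable difference in percentage points by base risk. If overdose is to be analysed as a count, say so and give its power on that basis.
3. In the triangulation paragraph, have a non-significant result for a low-powered binary outcome reported as inconclusive, with its estimate and confidence interval, even when the qualitative data are also null. It should not be reported as evidence of no effect.

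No new data or design change is needed. The cost is a less favourable power statement for binary outcomes, and fewer firm conclusions of no effect in the joint displays.

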### Qualitative data analysis with START-C2H intervention cohort:

**Qualitative Analysis Plan:** We will use constructivist grounded theory (CGT) methods to develop grounded theories about the perceived relationships and pathways linking (or failing to link) the intervention and changes in primary and secondary outcomes (or lack thereof). CGT provides rigorous methods that will (1) foster *discovery*; (2) elicit *rich descriptions* of participants' experiences of primary and secondary outcomes and of each intervention component; (3) support the creation of *grounded theories* about *perceived pathways* through which these phenomena influence one another; and (4) support comparisons of #1-#3 by participant age gender etc. We will use 3 CGT stages: open coding, axial coding, and theoretical coding.

**Open coding:** The open coding stage is designed to develop a rich understanding of salient phenomena by systematically and comprehensively labelling and defining concepts of interest in the transcripts. In the open coding process, [name] and the GRA will iterate between developing code labels, code definitions, and codebooks independently (to enhance feasibility), and meeting to develop consensus (to enhance validity); they will double code every 3rd transcript. Line-by-line analyses, conducted in NVIVO, will both explore intervention components and primary and secondary outcomes, and also be open to discovering new phenomena that are salient to the aims.

**Axial Coding:** The purpose of Axial Coding is to develop high-level categories that are more abstract than the "open coded" phenomena, and are both internally coherent and distinct from one another. During Axial Coding, categories are defined, and their properties and dimensions identified (i.e., their characteristics and the ways in which they vary, respectively). The GRA and [name] will iterate between independent analyses of open-coded transcripts, and consensus building about emerging learnings. They will independently develop a Category Memo for each emerging category that (1) defines it; (2) identifies and defines its properties and dimensions and possible subcategories; (3) inventories associated codes; and (4) describes how the category differs from other similar categories under development. [name] and the GRA will meet weekly to review one another's emerging findings and memos, and develop a suite of consensus categories,

definitions, properties, and dimensions. Categories will be expanded as additional transcripts undergo open coding, and offer new evidence.

Theoretical coding: Theoretical coding is designed to develop grounded theories that describe how categories relate to one another along properties and dimensions. Here, grounded theories will explore the perceived pathways through which each intervention component is affecting each outcome, and also explore ruptures in anticipated pathways (e.g., perhaps FTS distribution does not seem to protect against overdose). We expect to have a separate grounded theory for each intervention component →outcome dyad. We will start with foundational analytic questions, drawn from CGT: *What are the perceived pathways through which specific intervention components “Cause” change in specific outcomes? What Contingencies must be present for these pathways to operate? What Conditions rupture the pathways linking an intervention component to an outcome?* [name] and the GRA will start by examining 3 axially coded transcripts for participants' perspectives on answers to these questions, developing “relational statements” that provisionally answer them. *Relational Statements* succinctly describe relationships between or among two or more categories along their properties and dimensions. We will test each relational statement using a chart, in which each axis is a property that ranges along a particular dimension. In some cases, participants will have “off diagonal” experiences. These “off diagonal” participants are opportunities to deepen the analysis by exploring whether categories or their posited relationships need to be amended. Learnings will be recorded in Relational Memos.

We will use the constant comparison method to systematically compare findings across participant subgroups (e.g., defined by gender, houselessness status). To support these comparisons, we will color-code each relational chart by these subgroup characteristics. When we find variation across subgroups, we will return to the data to identify conditions and contingencies that may explain these variations, and expand relational statements accordingly, or the categories they link. As needed, we will present different sets of relational statements for specific subgroups. These relational statements will form the foundations of grounded theories exploring perceptions of each intervention component's effect on each outcome, and the pathways through which it does (or does not) operate to change primary and secondary outcomes, for particular subgroups.

Triangulating across qualitative and quantitative findings: We will use joint displays to systematically compare and contrast qualitative and quantitative findings for each intervention component/outcome relationship (e.g., preliminary [i.e.,  $p < 0.10$ ] hypothesis test results about the relationship of receiving FTS to subsequent overdose vs. qualitative grounded theory about this same relationship). When qualitative and quantitative findings both suggest an ameliorative relationship, we will conclude that the available evidence supports a beneficial effect. When both find an adverse relationship, we will conclude that the evidence indicates a harmful effect. When neither suggests a relationship, we will conclude that the evidence indicates no effect. When quantitative and qualitative results diverge, we will return to the qualitative and quantitative data to learn if we can resolve this discrepancy. Qualitative data may illuminate an unexpected confounder for the quantitative hypothesis test. Alternatively, qualitative data may suggest that the intervention only has an effect in one subgroup (e.g., individuals residing in counties with more services) and the quantitative findings reach a null conclusion because the quantitative sample is small, and includes both people who do and do not live in such counties. We will seek to systematically explore all divergences using these tables, and seek to refine relational statements and grounded theories accordingly. We will rely solely on qualitative data to learn whether the intervention effect is attenuated in a subgroup (e.g., women), given that the quantitative sample is underpowered to detect effect moderation.
